Patients who do not meet the inclusion criteria may remain in conventional hospitalization and should be re-evaluated. Patients who are classified as "red" have priority admission to the ICU, followed by those classified as "yellow". Patients classified as "blue/black" remain in conventional hospitalization and receive palliative care with active medical therapy at the discretion of the attending physician and according to the opinion of the patient and/or family. Patients should be re-evaluated on days 2 and 5 and re-classified. Decisions beyond day 5 in icu will depend on the availability of resources (these criteria are those dictated by the Spanish Society of Intensive Care Medicine (Semicyuc) for ICUs).

For the donor:

1. Ability to understand the HIP and sign the IQ of the study.
2. Age equal to or greater than 18 years.

3. Compliance with the criteria to be accepted as a plasma donor according to European and Spanish regulations (RD 1088/2005).
4. Presence of IgG antibodies **against SARS-CoV-2 delectables in peripheral blood 50 UA/mL.**
5. Absence of COVID-19 symptoms in the last 14 days.
6. NEGATIVE SARS-CoV-2 RT-PCR in at least one nasopharyngeal sample.
7. Weight over 50 kg and good venous access.
8. Acceptance for the conservation of serum library samples for the realization of antigranulocyte antibodies; especially in cases in which the recipient presents respiratory clinic.

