4.2.6. Plasmapheresis of ex-convalescent donors

1. On the day of the appointment, a confirmation will be made that the selection criteria have not changed, and it will be confirmed that the analytical tests are correct.

2. Blood pressure, temperature and heart rate will be taken. Donors with a temperature greater than 37.0°C will not be accepted. Hyper/hypotensive, tachycardia or bradycardia donors will be accepted at the discretion of the Haematologist responsible for the extraction.

3. The donation will be assigned a SIN (Single identification Number; or number of donation).

4. Each of the extraction bags and the documentation related to this donation will be labelled with this NUMBER WITHOUT.

5. An extraction of 600 mL of plasma without leukocytes (< 1 x 10⁶ leukocytes per unit extracted) shall be carried out using any apheresis machine with its corresponding validated sets or kits (CE Marking) for the extraction of plasma for transfusion use. The specific protocol of each commercial house will be used.

Due to the new orders of the Ministry of Health, the Blood and Tissue Bank of the Balearic Islands will be in charge of the treatment of the sample (inactivation, classification, plasmapheresis and sending to the relevant centre). This institution is responsible for generating a plasma bank with anti-SARS-CoV2 antibodies from ex-convalescent COVID-19 donors. These donors will be selected by the Blood and Tissue Bank of the Balearic Islands as Son Llàtzer University Hospital, who will make the extractions and send the sample for treatment to the Blood and Tissue Bank. The apheresis product obtained in Son Llàtzer University Hospital shall be used as a priority in Son Llàtzer University Hospital. For the rest of the participating centres, apheresis products from the plasma bank of the blood and tissue bank will be used.

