4.2.7 Processing of plasma units

(IMPORTANT: the rules of the document *RECOMMENDATIONS FOR OBTAINING PLASMA FROM CONVALESCENT DONORS OF COVID-19* of the Ministries of Health will be followed[24])

1. The plasma units (identified with the SIN) will be stored at 20°C (butanediol plates, or similar) if they are to be processed before 8h; or frozen (< -20°C) if they are going to be processed after 8h.
2. Before the pathogen inactivation process, the 600 mL units shall be separated into two 300 mL bags; using sin as traceability. Each of the 300 mL bags is labelled with the SIN followed by subcode 01 and 02.
3. The 300 mL bags shall be subjected to a pathogen reduction process (inactivation), using any pathogen inactivation system validated for the treatment of plasma for transfusion use. The inactivation process will be carried out in accordance with the specific procedures of each commercial house.
4. If the plasma has been previously frozen, it shall be thawed, inactivated and re-frozen within a period of not less than 2h.
5. All processes, from plasma extraction to final storage after inactivation, shall be carried out maintaining a closed system to ensure the sterility of the product, using a sterile tube connection system, validated for the use of transfusion products. Handling of products within a flow chamber as a closed system is not accepted.

-Labelling of plasma units of convalescent donors

1. Inactivated units will be labelled using the SIN code and subcode 01 or 02.
2. The labelling of devices shall preferably follow the criteria set out in the ISBT128 coding of blood products. The labels will include all the information required for any blood product according to the European guidelines¹.
3. Product coding will ideally be done by assigning a new ISBT128 product code that identifies plasma units as specific from COVID19 convalescent donors. The product codes will be:
 - E9746 = Apheresis CONVALESCENT PLASMA| NS/XX/<=-25C| Riboflavin-treated| COVID-19
4. In addition, the labels shall include the following information specific to that investigation product:
PLASMA FROM ALTRUISTIC DONORS CONVALESCING FROM COVID-19
INVESTIGATIONAL PRODUCT FOR USE EXCLUSIVELY WITHIN THE CONPLAS-19
CLINICAL TRIAL
SARS-CoV-2 RNA PCR NEGATIVE; SARS-CoV-2 IgG POSITIVE
STORAGE AND DISTRIBUTION OF PLASMA UNITS FROM CONVALESCENT DONORS

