2.3 DESCRIPTION

PREVIOUS ACTIONS

1. The donor will be summoned a week before by the Secretary of haematology, after management of the haematologist responsible for the identified patient-donors (either from donors who come from internal medicine or haematology)

ACTIONS

2. Interview with the doctor, in which we will proceed to:
 1. Inform the objective of the study and the phases of it.
 2. Report complications arising from the procedure and request informed consent.
 3. Perform the standard pre-donation interrogation of plasma derivatives.
 4. Make analytical requests:
 1. Group ABO, Rh (D) and irregular antibodies.
 2. Blood count, biochemistry including total proteins, liver tests, determination of immunoglobulin levels
 3. Serology: chronic HBV profile; Hepatitis C, antibodies; HIV (1+2), antibodies and/or antigen; lue profile.
 4. Determination of COVID19 antigenemia. It will be made in a petition that will include description "donor plasma protocol COVID-19"
5. Weight greater than 50 kg should be checked at the interview. The donor should be advised to avoid eating high-fat meals 12 hours before donation. The haematologist will perform the patient assessment for the extraction of 600 ml of plasma.
6. Information will be collected from the donor on whether he takes regular medication, mainly ACE inhibitors. At the end, an email will be sent to Microbiology ([contact]) with the history number and the names and surnames of the donors of the day, to carry out the Covid19 serology test quantitatively.

7. Nursing assessment of the state of the patient's veins.
8. Blood draw by nursing for the requested tests:
 1. Hand washing with soap and water or hydroalcoholic solution.
 2. Placement of disposable gloves.
 3. Place the compressor on the selected arm, select the most suitable vein for venipuncture.
 4. Disinfect the puncture area as standard.
 5. Label the extracted tubes and fill in the requests.

SUBSEQUENT ACTIONS

1. After the verification of the requested tests, by the haematologist who performs the interview, the donor will be summoned in apheresis by the Secretary of haematology, through the coordination of the responsible haematologist and the supervisor of the service. At this time clinical trial coordination will inform

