3.4 DESCRIPTION

PREVIOUS ACTIONS

It is important to notify the haematologist of the Transfusion Centre (BSTIB) on the same day that the appointment for plasmapheresis is confirmed for the correct scheduling of the treatment of the component, which includes the technique of reducing plasma pathogens, the analysis of the donation unit and the freezing of the two units obtained until their distribution.

1. We will present ourselves upon the arrival of the donor and inform us of the procedure to which he will be subjected.
2. We will check that the donor has correctly signed the informed consent and the screening questionnaire.
3. We will check that all the analyses requested in the baseline consultation have been carried out (ABO and RH EAI group, biochemistry with liver function, blood count, serology: HBV, HCV, HIV, treponema). In case of doubt with the results comment with haematologist responsible for the extraction)
4. Wash hands with soap and water or hydroalcoholic solution.
5. Glove placement
6. Taking ta, T^a, FC, weighing and carving the donor. The extraction should not exceed 13% of the donor's volume (70 kg, can extract 637 ml; 50 Kg 455 ml).
7. Assembly of the equipment: (before assembly confirm that the protocol card that we have to use for plasma collection and pump adapters is inserted into the machine).
8. The procedure is a single puncture (a single route), using the PPP protocol with filter (*Platelet Poor Plasma*; Platelet-Poor Plasma) and the necessary material is as follows:
 1. The plasmapheresis team. Plasma equipment for the PPP protocol (792P)
 2. ACD anticoagulant solution of 500 ml.
1. Preparation of the apheresis machine:
 1. Once the MCS+ is started, the detected protocol card will be shown on the screen.
 2. A series of checks will automatically be carried out on all the safety components of the MCS+.

3. Select Protocol: LNG25B/1BD6
4. The operator must close, open and re-close the centrifuge cover for checking check that the centrifuge adapter is on.
5. The possibility of choosing between two disposables will appear on the screen, with the MODIFY key we will move through the options. We will use the EXTRACT key to select the disposable **792P**.
6. We will install the disposable as indicated on the screen of the MCS+, first we will insert the bowl, making sure of its correct installation, to avoid any type of friction, we will close the lid and pre-install the tube of the blood pump.

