3.7 RELATED FILES

Annex 5 : **Immune plasma collection record sheet** .

Annex 4: Request for processing, inactivation, freezing and distribution of COVID-19 convalescent plasma.

4. PROCESSING OF THE COVID-19 PLASMA UNIT in the FBSTIB ONCE RECEIVED AFTER ITS EXTRACTION.

The procedure will be carried out using personal protective equipment (PPE) and the cleaning and disinfection measures of the laboratory area.

[figure not shown]
The steps to follow are:

1. Reception of the convalescent plasma unit
2. Check documentation and inactivation request:
3. Check end time collection
4. Single identification number (SIN): Check that additional codes have been sent (minimum 4 per 600 mL unit)
5. Each 600 mL unit shall be allocated in 2 300 mL units (refer to the FR-FRA-XX aliquot procedure)
6. Add transfer bag equipment using sterile sealant.
7. Label each satellite bag with an additional code and add subcode 01 and 02.
8. Aliquoted by gravity distributing a volume of between 250 and 300 mL in each aliquot.
9. Add the inactivation equipment to each aliquot and attach the corresponding numbering to the final bag.
10. Proceed to plasma inactivation according to usual procedure (PR-FRA-62)

Product obtained: **E9746 Plasmapheresis of convalescent plasma COVID-19, treated with riboflavin, aliquot 1 and Aliquot 2**

11. Freeze in quick freezer before 8 hours from the time of collection (PR-FRA-68)
12. Once frozen, the hospital transfusion service that sent it for collection will be contacted
13. If collection by the hospital transfusion service is delayed, it shall be stored in a separate room, segregated from the transfusion plasma of normal donors.
14. Add the conditions of carriage (refer to the distribution procedure PR-DIS-XX)

Initial Product	Transformation	Final Product	
E5293V00	114	E5293VA0	E5293VB0
E5293VA0 (52931)	118	E9746VA0 (97461)	
E5293VB0 (52932)	119	E9746VB0 (97462)	

BIBLIOGRAPHY

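### A 600 mL collection with no weight condition conflicts with the annex's 13% cap for donors between 50 and about 66 kg, and the annex's 250 to 300 mL aliquot range does not match the fixed 2 x 300 mL dose

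*Combined protocol and SAP*

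**What the plan says.** **Collection volume.** Section 4.2.6 requires "An extraction of 600 mL of plasma without leukocytes" and attaches no weight condition. Annex VIII assumes the same volume: section 2.3 says "The haematologist will perform the patient assessment for the extraction of 600 ml of plasma", and its later sections refer to a 600 mL bag.

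**Donor weight.** Section 4.2.1 lists "Weight over 50 kg and good venous access" as a donor criterion. Annex VIII, section 2.3, repeats it: "Weight greater than 50 kg should be checked at the interview".

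**Cap.** Annex VIII, section 3.4, states "The extraction should not exceed 13% of the donor's volume" and illustrates it with "70 kg, can extract 637 ml; 50 Kg 455 ml". The kind of volume is not named.

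**Split and dose.** Section 4.2.7 says "the 600 mL units shall be separated into two 300 mL bags". Sections 4.1 and 4.2.4 give the recipient two infusions of 300 mL, 600 mL in total. Annex VIII, section 4, first asks for two 300 mL units and, three steps later, says "Aliquoted by gravity distributing a volume of between 250 and 300 mL in each aliquot".

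**Source and records.** Section 4.2.4 prefers one donor for the 600 mL but allows different donors, and asks for the final titre of the two doses to be recorded. Its accounting form lists patient code, unit code, expiry date and administration date.

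**The concern.** Each of these instructions reads sensibly alone, but they do not fit together. If the cap rises in proportion to weight, there is a band of eligible donors for whom the main protocol and its annex cannot both be followed.

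Two things are at stake. The first is donor protection: staff who follow section 4.2.6 to the letter would exceed a limit stated in the same document. The second is knowledge of the dose. Infused volume could vary between recipients, and neither the accounting form nor the variable list in section 4.3.3 has a field for it. A secondary objective in section 3.2.2 asks how the donor's antibodies influence the recipient's course. The amount of antibody delivered depends on volume as well as titre, so an unrecorded difference in volume would blur that analysis.

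**Working it through.** **Inputs.** Cap of 13% with examples of 637 mL at 70 kg and 455 mL at 50 kg (Annex VIII, 3.4). Collection of 600 mL (4.2.6). Donor weight above 50 kg (4.2.1; Annex VIII, 2.3). Aliquots of 250 to 300 mL (Annex VIII, 4). Dose of 2 x 300 mL (4.1, 4.2.4, 4.2.7).

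**Step 1: reproduce the annex's figures.** Implied donor volume per kg = limit / 0.13 / weight.
- 637 / 0.13 / 70 = 70 mL/kg
- 455 / 0.13 / 50 = 70 mL/kg

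So the cap is 0.13 x 70 = 9.1 mL/kg. Putting it back, 9.1 x 70 = 637 and 9.1 x 50 = 455, both exact. The two examples agree with each other, so a slip in one of them is not the explanation.

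**Step 2: lowest weight at which a volume fits the cap.** Weight = volume / 9.1.
- 600 mL: 600 / 9.1 = 65.9 kg
- 500 mL (2 x 250 mL): 500 / 9.1 = 54.9 kg

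**Step 3: the two alternatives for a lighter donor.** Excess = 600 minus cap. Aliquot = cap / 2.

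| Weight (kg) | Cap (mL) | Excess if 600 mL is taken | Each of two aliquots if the cap is kept (mL) |
|---|---|---|---|
| 50 (boundary, not itself eligible) | 455.0 | 145 mL, 32% | 227.5 |
| 55 | 500.5 | 99.5 mL, 20% | 250.3 |
| 60 | 546.0 | 54 mL, 10% | 273.0 |
| 65 | 591.5 | 8.5 mL, 1% | 295.8 |
| 66 | 600.6 | none | 300.3 |

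The last two columns are alternatives: a given collection meets one or the other. Eligibility starts above 50 kg, so the excess for an eligible donor stays just under 32%.

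**Step 4: the aliquot range, at any donor weight.** The lowest total that Annex VIII, section 4, permits is 2 x 250 = 500 mL. Against the stated 600 mL, 1 - 500/600 = 16.7%. This mismatch does not depend on the cap. It applies equally to a donor of 70 kg or more, for whom a shortfall is permitted but not forced.

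**The case against.** The natural defence is that 600 mL is the target and 13% the individual ceiling. The haematologist assesses each donor for a 600 mL extraction, the donor is weighed before the machine is set up, and some machine settings can be changed during the procedure. That is a fair reading, but the text does not state it. The assessment carries no weight threshold and no reduced volume, and nothing says whether a 58 kg donor is refused, gives less, or gives 600 mL.

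A second defence is that section 4.2.4 allows plasma from different donors, so a short collection need not become a short dose. This stands in part. The clause widens the source of plasma but gives no rule for topping up short bags: two short bags from two donors are still short. Using more donations would also strain the planning ratio in section 4.2.10 of one donation per recipient.

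A third concerns scope. Annex VIII is the coordinating hospital's procedure, dated before the multicentre version, and section 4.2.6 supplies other centres from the blood bank. The documents do not show that the cap governs the bank's own collections. That limits how far the cap conflict extends. It does not remove it for collections at the coordinating hospital.

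Three stronger readings are tempting, and the documents do not support them:
- A reader might infer that the cap is broken and the aliquots are also short. A full 600 mL collection divides into two nominal 300 mL bags, so for one donation these are alternatives.
- A reader might infer that recipients could receive as little as 455 mL, 24% below 600 mL (1 - 455/600). That takes a donor of exactly 50 kg, who is not eligible, and aliquots of 227.5 mL, below the annex's own 250 mL minimum.
- A reader might infer bias in plasma versus control. Volume varies only within the plasma arm, and nothing in the documents shows a mechanism for bias; at most an effect could be diluted.

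**Conclusion.** The documents contradict themselves on two points.

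First, the 600 mL collection and the 13% cap cannot both be followed for eligible donors between 50 and about 66 kg. Either the cap is exceeded, by up to just under 32%, or two 300 mL bags cannot be filled. Below about 55 kg two 250 mL bags cannot be filled either. Second, the 250 to 300 mL aliquot range does not match the fixed 2 x 300 mL dose and permits a total about 17% below it.

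The first result assumes that the cap scales in proportion to weight at 9.1 mL/kg, as both annex examples do. The second needs no assumption. How often either matters is unknown, because the documents give neither the share of donors under 66 kg nor the volumes actually infused. The consequence for the analysis is confined to the donor-antibody objective and to knowing what dose was given. This should be put right, but it does not undermine the comparison of the two arms.

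**What to change.** The sponsor should reconcile the following into one consistent set: the dose (4.1, 4.2.4), the donor weight criterion (4.2.1; Annex VIII, 2.3), the extraction volume (4.2.6), the split (4.2.7), the cap (Annex VIII, 3.4) and the aliquot range (Annex VIII, 4). The revised text should state what happens when the cap is below 600 mL and when a bag holds less than 300 mL, and whether the cap also applies to the blood bank's own collections. Which volume, weight or limit is right is for the sponsor to settle.

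Whatever is settled, add the actual infused volume of each unit to the accounting form in 4.2.4 and to the variable list in 4.3.3, next to the titre already recorded. The donor-antibody analysis can then take account of the volume delivered. Volume multiplied by titre is one option, not a requirement.

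The cost is amendment wording and one data field.

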3.5 POTENTIAL COMPLICATIONS

1. By the apheresis itself: vasovagal reactions, citrate poisoning, hypovolemia, haemolysis, chills and feeling cold.
2. Hypotension
3. Hypocalcaemia
4. Anxiety

3.6 RESULT CRITERIA

5. The donor will declare to be informed of the procedure to which he will be subjected.
6. Reduced donor anxiety
7. Apheresis is performed as safely as possible.
8. The donor will not suffer unnecessary risks.
9. Pre and post apheresis data will be recorded on each donor's registration sheet.
10. The product will be treated with maximum security for its transfer and processing.

3.7 RELATED FILES

Annex 5 : **Immune plasma collection record sheet** .

Annex 4: Request for processing, inactivation, freezing and distribution of COVID-19 convalescent plasma.

4. PROCESSING OF THE COVID-19 PLASMA UNIT in the FBSTIB ONCE RECEIVED AFTER ITS EXTRACTION.

The procedure will be carried out using personal protective equipment (PPE) and the cleaning and disinfection measures of the laboratory area.

[figure not shown]
The steps to follow are:

1. Reception of the convalescent plasma unit
2. Check documentation and inactivation request:
3. Check end time collection
4. Single identification number (SIN): Check that additional codes have been sent (minimum 4 per 600 mL unit)
5. Each 600 mL unit shall be allocated in 2 300 mL units (refer to the FR-FRA-XX aliquot procedure)
6. Add transfer bag equipment using sterile sealant.
7. Label each satellite bag with an additional code and add subcode 01 and 02.
8. Aliquoted by gravity distributing a volume of between 250 and 300 mL in each aliquot.
9. Add the inactivation equipment to each aliquot and attach the corresponding numbering to the final bag.
10. Proceed to plasma inactivation according to usual procedure (PR-FRA-62)

Product obtained: **E9746 Plasmapheresis of convalescent plasma COVID-19, treated with riboflavin, aliquot 1 and Aliquot 2**

11. Freeze in quick freezer before 8 hours from the time of collection (PR-FRA-68)
12. Once frozen, the hospital transfusion service that sent it for collection will be contacted
13. If collection by the hospital transfusion service is delayed, it shall be stored in a separate room, segregated from the transfusion plasma of normal donors.
14. Add the conditions of carriage (refer to the distribution procedure PR-DIS-XX)

Initial Product	Transformation	Final Product	
E5293V00	114	E5293VA0	E5293VB0
E5293VA0 (52931)	118	E9746VA0 (97461)	
E5293VB0 (52932)	119	E9746VB0 (97462)	

BIBLIOGRAPHY

